## Statement of the Problem

Cardiovascular disease (CVD) remains the most common cause of death in the United States. CVD currently claims nearly one million lives yearly in the U.S., accounting for nearly 40% of all deaths (1). The total cost of cardiovascular disease in the U.S., including hospitalizations and lost productivity, is approximately \$300 billion annually (1,2). Coronary artery disease (CAD) accounts for the largest number of deaths and the majority of these costs. While the efforts aimed at treating this disease in recent decades have concentrated on surgical and catheter-based interventions, limited resources have been directed toward primary prevention and rehabilitation (3,4).

Over the last decade, the use of percutaneous coronary intervention (PCI) has increased exponentially. Between 1996 and 2007, the number of PCIs performed in the U.S. increased more than 4-fold, from approximately 300,000 to more than 1.3 million yearly (1). During this time, PCI has accounted for 10% of the overall increase in Medicare expenditures (5). In light of the extraordinary increase in the use of this technology in recent years, questions have been raised regarding the cost-effectiveness of PCI, the extent to which PCI is overused, and whether selected patients may benefit from optimal medical therapy in lieu of PCI (5-9). Despite the fact that PCI is expensive, repeat PCI is not unusual (10) and there is no evidence for improved survival (11), alternative therapies are rarely considered. One alternative therapy that has been shown to improve outcomes in PCI candidates is intensive lifestyle intervention, including exercise training. In the PCI vs. Exercise Training (Leipzig) study (12), PCI candidates randomized to one year of exercise training had improved coronary anatomy, higher exercise capacity, an improvement in quality of life and event-free survival, as well as lower health care costs when compared to the PCI group. However, the Leipzig study employed invasive angiographic methods which do not provide information on dynamic coronary flow or atherosclerosis specifically, and do not provide insight into the mechanism of atherosclerosis progression or regression (13). In addition, economic analyses were limited to cost per change in Canadian Cardiovascular Society Class; the Leipzig study did not assess *cost-effectiveness*.

Given the high volume of PCI, its high cost, its lack of effect on survival and the potential for alternative treatments including exercise and risk reduction in PCI candidates, the current proposal is termed “**PCI Alternative Using Sustained Exercise**” (PAUSE). **The primary aim of PAUSE is to employ non-invasive methods to determine whether patients randomized to exercise intervention have greater improvement in coronary function and anatomy compared to those randomized to PCI.** Both groups will receive optimal medical management. We will also compare health care costs, symptoms, quality of life, and clinical outcomes between the two groups. At baseline and one year after randomization, patients will undergo an assessment of physical activity patterns and fitness using standardized questionnaires and maximal cardiopulmonary exercise testing (CPX). Patients will also undergo evaluation of coronary function and anatomy with positron emission tomography combined with computed tomographic angiography (PET/CTA). PET will be used to measure myocardial perfusion. CTA will be used to evaluate anatomical progression of atherosclerotic disease based on a qualitative scoring system of coronary artery calcium. The combination of PET/CTA provides information that previously could only be obtained invasively using coronary flow wires and invasive x-ray angiography. This will permit a non-invasive way to evaluate both functional and anatomical adaptations to exercise. Our overall objective is to demonstrate the utility of a non-invasive technology to document the efficacy of exercise therapy as an alternative treatment strategy to PCI for coronary lesions.

## **Key Questions and Hypotheses**

### **Key Questions**

- 1) Does exercise training favorably alter coronary anatomy and function as determined by non-invasive imaging techniques?
- 2) Can a program of exercise therapy improve outcomes (exercise capacity, symptoms, repeat hospitalizations, and quality of life) in patients with CAD that are equivalent or superior to PCI?
- 3) Will exercise training and intensive risk reduction reduce costs as compared to standard PCI after 1-year?

### **Specific Objectives**

Principal Objective. The principal objective of this proposal is to determine if a program of exercise training improves coronary function and anatomy measured by non-invasive imaging.

Secondary Objective #1. To compare the effects of exercise training to PCI on clinical and functional outcomes in patients with CAD.

Secondary Objective #2. To determine whether a 1-year program of exercise intervention will save health care costs compared to PCI.

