## RESEARCH DESIGN and METHODS

## Study Population

*Stable patients between the ages of 50 and 70 years who have lesions appropriate for PCI based on American Heart Association/American College of Cardiology criteria will be considered for the study. Only patients with a good prognosis (annual mortality <1% based on VA multivariate scores (56, 57) will be considered. Patients with left main disease or proximal LAD disease will be excluded. Additional exclusion criteria include those with unstable angina, a history of heart failure (EF ≤30%), pacemakers, atrial fibrillation, myocardial infarction within the last 3 months, diabetes, and those with orthopedic problems interfering with the ability to exercise regularly.*

**Recruitment.** *A study flow chart including screening, baseline evaluations, and procedures is presented in Appendix I. Subjects will be recruited from the following populations: 1) patients referred for a clinically-indicated stress myocardial perfusion study (nuclear, echo, or CT); and 2) patients who have a positive exercise test with >1.0 mm ST-segment deviation from baseline on a standard treadmill exercise test, estimated to have a >80% probability of disease based on VA scores (56,57). There are approximately 2,500 patients who undergo these evaluations for CAD at our facility annually, providing a large pool of potential subjects for the study. Potential subjects will be referred for PET/CTA, and baseline PET/CTA findings will confirm patients meet inclusion and exclusion criteria. If the PET/CTA studies show significant ischemia in a moderate to large territory supplied by a significantly diseased vessel, these patients will be recruited for the study.*

*PET is considered the gold standard for stress perfusion imaging. Thus, only patients who have moderate to large areas of moderate to severe perfusion defects will be recruited. In addition, only subjects who have a perfusion defect on PET supplied by a significantly diseased artery on CTA will be recruited. Only subjects actually referred for PCI will be considered for the study. A partial waiver of authorization (per HIPAA) will be obtained in order to access medical records or contact individuals for the purpose of study recruitment. A total of 64 subjects will be recruited; randomization will be stratified by age, exercise capacity, and BMI so that these variables will be matched evenly between exercise intervention and PCI groups.*

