### **PCI Group**

*The PCI group will be followed by their cardiologist and will receive usual clinical care. Subjects in both groups will be Veterans who receive their routine care at our facility, so it will be easier to gather pertinent information and to ascertain that subjects in both groups are receiving optimal medical therapy (including blood panels and blood pressure every 4 months). The testing schedule, timelines, and all procedures (except exercise training and PCI) will be similar between the PCI and exercise groups. Physical activity patterns will be monitored in a similar fashion in both the PCI and exercise groups. At each 4 month visit, the Co-PI ([name]) will review the overall adequacy of care for each subject in the study.*

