### ***Statistical Analysis Plan***

***Key Question #1:*** Does exercise training favorably alter coronary anatomy and function as determined by non-invasive imaging techniques?

***Statistical Analysis, Key Question #1.*** Myocardial blood flow using PET at rest and following dipyridamole infusion will be expressed as ml flow/100 g/min. The primary outcome, myocardial perfusion reserve, will be calculated as the ratio of the myocardial blood flow during stress (e.g. after dipyridamole) and the myocardial blood flow at rest. Differences within and between groups will be assessed using repeated measures ANOVA, with group (exercise vs. PCI) and test (baseline vs. 1-year) as factors. Post-hoc procedures will be performed using the Bonferonni method.

***Key Question #2:*** Can a program of exercise therapy improve outcomes (exercise capacity, symptoms, repeat hospitalizations, and quality of life) in patients with CAD that are equivalent or superior to PCI?

Statistical Analysis, Key Question #2. These secondary outcomes will include changes in peak  $VO_2$  and other cardiopulmonary exercise test responses (including  $VO_2$  at the ventilatory threshold, exercise time, and heart rate recovery), quality of life measures, and lipid panels. Paired tests will be used (paired t-test or Wilcoxon signed rank test) to compare continuous variables between groups at baseline. Differences between groups after the 1-year study period will be assessed by repeated measures ANOVA, with group (exercise vs. PCI) and test (baseline vs. 1-year) as factors. Post-hoc procedures will be performed using the Bonferroni method.

**Key Question #3:** Will exercise training reduce costs as compared to standard PCI after 1-year?

Statistical Analysis, Key Question #3. Comparison of costs will be made for the individual level change scores using the intervention net-costs (intervention delivery minus healthcare expense cost-savings). Cost effectiveness of the intervention will be defined by the primary outcome at the patient level. That is, changes from baseline in individual global myocardial perfusion reserve using PET at 1-year will be used to calculate the effect. Differences in costs between groups will be assessed using ANOVA.

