### **Sample Size Estimates**

*Sample size estimates are based on our primary endpoint, change in global myocardial blood flow reserve from baseline using pharmacologic stress with dipyridamole, and applying variance in myocardial blood flow reserve measured by PET published previously in subjects with coronary artery disease (71,77,78). We anticipate that the overall change in the primary endpoint will be approximately 15%; this is based on previous measurements of coronary blood flow reserve using PET comparing sedentary and fit subjects cross-sectionally (77), after exercise training (78), and risk reduction interventions such as smoking cessation (96). We also anticipate that these changes will parallel the well-documented changes in exercise capacity with training in subjects with CAD (i.e. mean change in peak  $VO_2 \approx 15\%$ ) (18,19,24). Given a standard deviation of myocardial flow reserve in similar populations of 0.20 ml/g/min both at baseline and after treatment with a pre-post correlation of 0.65 (calculated from the data in reference 96), the standard deviation of the change in myocardial blood flow is 0.167. We want to detect a 15% change (absolute change of  $0.15 \times 0.9$  or 0.135) so the standardized effect size (absolute value of difference in group values for mean change divided by the standard deviation) is about 0.81. Using a 2-sided significance level of 0.05 and 80% power, 25 subjects in each group will be needed to complete the protocol.*

We anticipate that there will be a 20% dropout rate, which is typical of that in the cardiac rehabilitation literature and in accordance with our previous experience. Thus, our target enrollment will be 32 subjects in each group. The dropout rate may be lower given that compliance tends to be better in research studies compared to clinical practice, and that the subjects will receive continuous monitoring, follow-up, and encouragement to remain physically active. *Dropouts will not be included in the statistical analyses (97).*

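### The principal objective and Key Question #1 name no comparator, and the SAP does not say that only the randomised exercise-versus-PCI difference in change answers them

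*Combined protocol and SAP*

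**What the plan says.** The protocol puts its main question in three ways.

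- **No comparator.** Specific Objectives: "The principal objective of this proposal is to determine if a program of exercise training improves coronary function and anatomy measured by non-invasive imaging". Key Question #1, repeated in the Statistical Analysis Plan: "Does exercise training favorably alter coronary anatomy and function as determined by non-invasive imaging techniques". By contrast, both secondary objectives and Key Questions #2 and #3 name PCI.
- **Better than PCI.** The Statement of the Problem gives the primary aim as to "determine whether patients randomized to exercise intervention have greater improvement in coronary function and anatomy compared to those randomized to PCI". Purpose of the Current Proposal repeats this for perfusion and function, and the hypothesis closing Significance of the Current Proposal is also comparative.
- **Similar to PCI.** The rationale in the PET/CTA Study Protocol section sets out to show that exercise improves perfusion about as much as PCI does.

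For Key Question #1 the SAP says "Differences within and between groups will be assessed using repeated measures ANOVA", with group (exercise, PCI) and test (baseline, 1 year) as factors and Bonferroni post-hoc procedures. It does not say which result settles the question.

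On background care, the Statement of the Problem says "Both groups will receive optimal medical management". The PCI Group section adds that the investigators will check that "subjects in both groups are receiving optimal medical therapy", with adequacy of care reviewed at each 4-month visit. There are two arms: exercise, and PCI with usual care. Under Study Population, "baseline PET/CTA findings will confirm patients meet inclusion and exclusion criteria", and Table 1 lists PET/CTA only at baseline and 1 year.

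**The concern.** A reader who takes the principal objective and Key Question #1 literally will look at the exercise arm's change from baseline, and the SAP supplies a test for it. That change contains any effect of exercise plus whatever medical management, time and repeat measurement contribute over the year. No arm shows what happens without exercise and without PCI, so these parts cannot be separated.

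The between-arm contrast does not isolate exercise either, because PCI is itself expected to raise perfusion. It does answer a clear randomised question: how exercise compares with PCI, both on top of medical therapy.

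What is at stake is the conclusion. As written, the report could state that exercise training improves myocardial perfusion on the strength of a within-arm rise, even if the randomised comparison showed no difference or favoured PCI.

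**Working it through.** **Inputs**, all from Sample Size Estimates unless noted: SD of flow reserve 0.20 at each time; pre-post correlation 0.65; reference level 0.9; target change 15%; two-sided 5% level; 80% power; 20% dropout. The PET/CTA rationale cites a 20% gain in perfusion reserve after exercise training (7 patients) and a 20% gain in perfusion after PCI.

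**1. The plan's own figure.**
- SD of change = 0.20 × √(2 × (1 − 0.65)) = 0.167.
- Target difference = 0.15 × 0.9 = 0.135. Effect size = 0.135 / 0.167 = 0.81.
- n per group = 2 × (1.96 + 0.84)² × 0.167² / 0.135² = 24.0, which rounds up to 25. The power by noncentral t at 25 per group is 0.80.
- Enrolment = 25 / 0.8 = 31.25, rounded up to 32 per group, 64 in total.

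The stated numbers reproduce. The effect size is defined on the difference between groups in mean change, so the trial is sized for the comparative question.

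**2. What the within-arm test needs.** With 25 completers, a paired t-test has 24 degrees of freedom and critical value 2.064. The smallest significant mean change is 2.064 × 0.167 / √25 = 0.069, and 0.069 / 0.9 = 7.7%. The test reacts to a rise of that size whatever its cause.

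**3. How often it is positive if exercise does nothing.** The probability comes from the noncentral t with 24 degrees of freedom and noncentrality = rise × √25 / 0.167. The background rises are assumptions, because the documents give none.

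| Assumed background rise | Absolute (× 0.9) | Noncentrality | P(within-arm test significant) |
|---|---|---|---|
| 0% | 0 | 0 | 5% |
| 5% | 0.045 | 1.35 | 25% |
| 10% | 0.09 | 2.69 | 73% |
| 15% | 0.135 | 4.04 | 97% |

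The last row assigns the plan's whole target effect to causes other than exercise, so it is an upper illustration.

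**4. How the two tests can part.** Suppose both cited 20% gains held for flow reserve in this trial. The within-arm change would be 0.20 × 0.9 = 0.18, with noncentrality 0.18 × 5 / 0.167 = 5.4, and the within-arm test would be significant more than 99% of the time. The expected between-arm difference would be 0, and that test would be significant 5% of the time. The SAP does not say which of these answers Key Question #1.

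**The case against.** The strongest reply is that the trial is already comparative where it counts. The bold primary aim, the stated purpose, the hypothesis and the sample size all concern exercise against PCI, and the planned ANOVA has group as a factor. Nowhere do the documents say that a within-arm rise decides Key Question #1. This stands, and it limits the point to an inconsistency and a missing decision rule. It does not remove it: the statement labelled as the principal objective and the question heading the primary analysis both say something else.

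A second reply is that the background rises are not in the documents. That also stands. The smoking-cessation study cited among the sources for the 15% is not a measure of medical management, and patients are already in routine care at the facility, so how much therapy would still change after baseline is unknown. The figures show sensitivity; they are not a forecast.

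A reader might go further and infer that the baseline values must rebound, because the scan used for entry is also the baseline of the endpoint. The documents do not support that. Entry depends on the extent and severity of regional defects and on a diseased vessel on CTA, whereas the endpoint is global flow reserve. Any rebound depends on error shared between those measures, which is unknown. The 0.65 correlation is calculated from a risk-reduction intervention study and is not a test-retest figure; the repeat-study slopes quoted for PET (0.98 and 0.96) suggest little rebound. It is possible, of unknown size, and not needed for the argument.

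A reader might also infer that the lack of a medical-therapy-only arm is a design fault. The trial was built to test an alternative to PCI, and two arms suit that question.

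**Conclusion.** The point holds as a mismatch between the principal objective and Key Question #1 on one side and the design, stated aim and sample size on the other, together with an unstated decision rule. A within-arm rise cannot be credited to exercise here, since medical management runs alongside it and no arm has neither exercise nor PCI. That conclusion needs no numerical assumption.

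Its size does. Under the plan's SD and 25 completers, any mean rise of 0.069 or more is significant, and with no exercise effect the within-arm test is positive about 25% to 97% of the time across assumed background rises of 5% to 15%.

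The documents do not support reading this as a flaw in the randomised comparison. Background care and selection on the scan apply to both arms, and 25 completers and 32 enrolled per arm stand.

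**What to change.** 1. In Key Questions, Specific Objectives and the SAP, reword the principal objective and Key Question #1 as the comparison already given in the Statement of the Problem and Purpose of the Current Proposal: whether the 1-year change in global perfusion reserve is greater with exercise plus medical therapy than with PCI plus medical therapy.
2. Reconcile this with the PET/CTA rationale, which aims at similarity to PCI. The present sample size is for detecting a difference, so a non-significant difference would not establish similarity.
3. In the SAP, name the group-by-test interaction, which is the between-arm difference in change, as the single primary test and the only result that decides Key Question #1.
4. Report within-arm changes with confidence intervals as descriptive, with no claim that exercise caused them. Removing within-arm p-values alone would achieve nothing, since a 95% interval that excludes zero is the same test. What matters is the rule in item 3.

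The cost is wording only: no extra patients, scans or data. The downside is that the sponsor gives up a stand-alone claim that exercise improves perfusion.

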## **BACKGROUND**

### **Rationale for the Current Proposal**

Despite advances in treatment options for CVD, this condition remains the leading cause of morbidity and mortality in the U.S. and is a major cause of disability in Veterans (1). PCI is the treatment most often used in patients with various manifestations of CAD. It is often used as an intervention for those experiencing *acute coronary syndrome* (ACS), an umbrella term that describes a group of clinical symptoms associated with acute myocardial ischemia. PCI usually involves coronary angioplasty with permanent placement of a stent. This procedure has been shown to reduce symptoms due to CAD and to reduce ischemia (11). In recent years, drug eluting stents (DES) have been shown to reduce the high re-stenosis rate associated with bare metal stents (BMS). However, the cost of DES is 3 to 5 times higher than BMS and requires long term antiplatelet therapy (14). While it is commonly assumed that PCI also reduces mortality, randomized trials have shown that PCI has no effect on 1- to 5-year mortality except in patients being treated for acute myocardial infarction (6,11,15).

There have been major increases in the use of PCI over the last decade, with major costs associated with it. In a recent sub-study of the COURAGE trial, a VA Cooperative study comparing PCI to optimal medical therapy in 2,287 patients with chronic stable angina, the added cost of PCI versus optimal medical therapy was approximately \$10,000, with no benefit in terms of life-years or quality-adjusted life years gained (16). In another sub-study of COURAGE focusing on the effect of PCI on quality of life, it was demonstrated that the cost for 1 patient to have a clinically significant improvement in angina exceeded \$100,000 (17). The COURAGE results demonstrate that it is safe to defer PCI in patients with symptomatic chronic coronary disease, and deferring PCI achieves an appreciable savings in health care expenditures. In light of recent trials demonstrating benefits in coronary vascular function, coronary risk, and cost savings attributable to exercise training in patients with stable symptomatic CAD (12,18,19,20), it is possible that the addition of an exercise program to optimal medical therapy in PCI candidates would result in even better outcomes and cost savings.

Cost analyses have suggested that the current rate of increase in PCI with DES is unsustainable for the U.S. healthcare system (5). Given the high costs associated with PCI, there have been recent efforts to compare outcomes and effectiveness of PCI against non-invasive therapy. In the Occluded Artery Trial (OAT) (21), cumulative 2-year costs were \$7,000 lower in patients randomized to medical therapy versus PCI, and medical therapy was associated with slightly better quality-adjusted survival. In the primary COURAGE trial (6), PCI did not reduce the risk of mortality, myocardial infarction, or other cardiovascular events when compared to optimal medical therapy over 4.6 years of follow-up. Interestingly, in an additional sub-analysis of COURAGE assessing myocardial perfusion data (22), a greater improvement in percent of ischemic myocardium, a predictor of mortality, was observed in patients who underwent PCI. Although the myocardial perfusion results were conflicting to the main trial results, not all patients had myocardial perfusion evaluations performed and the sample in the sub-study was not randomized. In addition, the study did not include an evaluation of endothelial dysfunction, which has been associated with cardiac events and has been reported in post-PCI patients with DES. The COURAGE trial has stimulated a great deal of media attention and numerous commentaries. Interpretations of the COURAGE results range from confirmation of PCI as it is presently indicated by recognized guidelines, to recommending a greater emphasis on aggressive medical and lifestyle therapy in selected patients in lieu of PCI, to predicting a marked decline in PCIs (7,9,23).

There is a need to evaluate more judicious use of PCI, and to consider less costly interventions for at least some of the more than 1.3 million patients in the U.S. who undergo this procedure each year. Lifestyle intervention, including exercise training, is one option that has been shown to result in reduced symptoms, better exercise tolerance, improved quality of life and lower mortality (18). A growing body of data has demonstrated that exercise intervention improves coronary anatomy and lessens ischemia through enhanced endothelial function (12,18,19,24). While a significant proportion of health care expenditures are devoted to PCI and other invasive interventions for CVD, few health care resources are directed toward primary or secondary prevention. Recent studies have demonstrated that programs of cardiac rehabilitation, with and without implementation of intensive risk reduction, are cost effective (18,20). We (25) and others (26) have observed that higher physical activity patterns, higher levels of fitness, or both, are associated with lower health care costs. Recent prospective trials such as the INTERHEART (27) and HALE (28) studies, and long-term observational studies including the Nurses' Health Study (29), the Health Professionals Follow-up Study (30), and the Veterans Exercise Testing Study (VETS) (31,32), have shown that lifestyle factors, including physical activity, fitness, smoking cessation, and dietary intervention have a major impact on cardiovascular and all-cause mortality. In the INTERHEART study, a case-control evaluation of risk factors for acute myocardial infarction in 52 countries, it was demonstrated that 9 preventable risk factors explained 90 and 94% of the incidence of myocardial infarction in men and women, respectively (27). Importantly, simply removing smoking as a risk factor, adding a modest amount of weekly exercise (approximately 30 minutes/day), and including fruits and vegetables in the diet led to an approximate 80% lower risk of cardiac events. These results were similar to those from the Nurses' Health Study, which demonstrated that 75% of the risk for MI or stroke would be removed by these 3 risk factors in women (29).

Only one randomized, controlled study has compared exercise and lifestyle intervention with PCI. Hambrecht and colleagues (12) studied 100 candidates for PCI who were randomized to either one year of at-home rehabilitation or to PCI and standard medical therapy (the PCI vs. Exercise Training [Leipzig] Study). The subjects underwent baseline and repeat cardiac catheterization, maximal exercise testing, assessment of quality of life, and an analysis of the cost-effectiveness of each treatment. After one year, patients randomized to the exercise training group had improved coronary anatomy, higher exercise capacity, an improvement in quality of life, better event-free survival, and lower health care costs when compared to the PCI group. In a 2-year follow-up to this study, the event-free survival rate remained significantly lower in the exercise group compared to the PCI group, and inflammatory markers were significantly reduced in those

randomized to exercise. Many studies have demonstrated favorable effects of exercise training on endothelial function in the upper and lower limbs, including endothelial-dependent vasodilation, arterial flow reserve and other measures of vascular health (18,19,24). Hambrecht et al (19) were the first to demonstrate that supervised exercise training in patients with CAD improves endothelial-dependent vasodilation in the *coronary vessels*.

